3.2.1.7 Dose increment

Any dose change/delay flagged in the DAR eCRF page, satisfying the following criteria:

- a reason other than "as per protocol",
- a nonzero actual dose above any previous nonzero actual dose,
- a nonzero actual dose above the treatment assigned as per safety set.

The following criteria will be used to identify an **intra-patient dose escalation:**

- dose change flag checked with reason "as per protocol",
- planned dose above any previous planned dose.

3.2.1.8 **Cumulative dose**

Cumulative dose of a study treatment is defined as the total dose given during the study treatment exposure.

The actual cumulative dose for study treatment (PDR001) is defined as the total actual dose for this study treatment administrated, over the duration for which the subject is on the study treatment as documented in the DAR eCRF.

The following algorithms will be used to calculate the actual dose per one infusion in mg:

For weight based dosing: Actual dose (mg) = (Calculated dose prescribed, mg) \times (Total volume administrated, ml) / (Total volume constituted, ml)

• For flat dosing: Actual dose(mg) = (Dose prescribed, mg) × (Total volume administrated, ml) / (Total volume constituted, ml)

These parameters used for calculation ('Calculated dose prescribed', 'Dose prescribed', 'Total volume constituted', 'Total volume administered') will be collected on the DAR eCRF page. For patients who did not take any of study treatment, the actual cumulative dose is by definition equal to zero. Actual cumulative dose will then be calculated as the sum of actual dose per one infusion for all infusions.

The **planned cumulative dose** is defined as the total dose planned to be given as per the protocol up to the last date of study treatment administration. It is calculated in mg as:

- For weight based dosing: Planned cumulative dose (mg) = sum of (Calculated dose prescribed, mg) for all infusions
- For flat dosing: Planned cumulative dose (mg) = sum of (Dose prescribed, mg) for all infusions.

Similarly, 'Calculated dose prescribed' and 'Dose prescribed' will be collected on the DAR eCRF page. The planned cumulative dose is not summarized/listed. It is used for relative dose intensity calculations.

3.2.1.9 Dose intensity and relative dose intensity

For PDR001, the dose intensity (DI), expressed as mg/day, for patients with non-zero duration of exposure is defined as follows:

Dose intensity (DI) (mg/day) = actual cumulative dose (mg) / duration of exposure (days).

Planned dose intensity (PDI) (mg/day) = planned cumulative dose (mg) / duration of exposure (days).

Relative dose intensity (RDI) is the actual DI divided by the PDI, i.e. RDI = DI(mg/day) / PDI(mg/day).

For patients who do not take any study treatment, the actual cumulative dose is by definition equal to zero.

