#### 6.1.1 Dosing regimen

**Table 6-1 Dose and treatment schedule**

Study treatments	Pharmaceutical form and route of administration	Dose	Frequency and/or Regimen
PDR001	Powder for solution for infusion	1 mg/kg (starting dose)	Every 2 weeks (or alternative regimens, e.g. Q3W, Q4W)

PDR001 will be administered via i.v. infusion over 30 minutes (up to 2 hour, if clinically indicated) once every 2 weeks. The next dose may be delayed by up to 7 days to recover from previous AEs (see [Section 6.3.2](#)) before receiving the next dose. If the next dose cannot be administered within the above mentioned 7-day delay, then the dose should be skipped. Dosing will resume at the next scheduled dose and assessment schedule will be shifted accordingly. Dose modifications should follow [Section 6.3.1](#) and [Section 6.3.2](#).

If a significant number of patients require dose delays due to PDR001-related toxicities, or if the PK data support it, the dosing regimen for the study may be changed to once every 28 days. This will be discussed in a dose escalation teleconference at the time of the proposed change and documented in the meeting minutes accordingly (see [Section 6.2.3](#)). Alternative dosing regimens may also be considered based on clinical toxicity and preliminary PK/PD and efficacy findings.

Once the RP2D dose and schedule are determined, patients from the dose escalation who have completed 4 cycles of treatment may be offered the option of switching to the RP2D (dose and schedule). If this change leads to an increase in the dose, then the patient must fulfill the criteria outlined in [Section 6.2.3.4](#) for inpatient dose escalation.

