**Table 6-2 Provisional dose levels**

Dose level	Proposed dose*	Increment from previous dose
-1**	0.3 mg/kg	-70%
1**	1 mg/kg	Starting dose
2	3 mg/kg	300%
3	10 mg/kg	333%

\*It is possible for additional and/or intermediate dose levels to be added during the course of the study Cohorts may be added at any dose level below the MTD in order to better understand safety, PK or PD. Multiple dose levels below the MTD may be evaluated simultaneously in order to obtain PK and PD data across a range of doses and to establish the RP2D.

\*\*Dose level -1 represents a treatment dose for patients requiring a dose reduction from the starting dose level. No dose reduction below dose level -1 is permitted for this study.

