### **10.3 Treatments (study treatment, concomitant therapies, compliance)**

The actual dose and duration in days of PDR001 treatment as well as the dose intensity (actual dose received/actual duration) and relative dose intensity (the ratio of dose intensity to planned dose/planned duration) will be listed and summarized by means of descriptive statistics by treatment group. Categories for relative dose intensity of PDR001 will be specified as  $< 0.5$ ,  $\geq 0.5 - < 0.75$ ,  $\geq 0.75 - < 0.9$ ,  $\geq 0.9 - < 1.1$  and  $\geq 1.1$ . The number and proportion of patients within each category will be presented by treatment group.

These per-patient summaries will, in turn, be summarized using descriptive statistics by treatment group.

Concomitant medications and significant non-drug therapies prior to and after the start of the study treatment will be listed by patient and summarized by ATC term and treatment group.

The reason for discontinuation from treatment will be summarized and listed, along with dates of first and last study drug, duration of exposure to PDR001 and date of discontinuation for each patient.

Compliance with the protocol will be assessed by the number and proportion of patients with protocol deviations. Protocol deviations will be identified prior to database lock and will be listed and summarized.

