3.2.1.5 Dose delay/interruption

Any dose change/delay flagged in the DAR eCRF page, satisfying the following criteria:

- a reason other than "as per protocol"
- a zero actual dose
- occurs between the first and last non-zero doses
- follows a nonzero actual dose.

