3.2.2 Study treatment

The duration of exposure, actual cumulative dose, dose intensity (DI) and relative dose intensity (RDI) will be summarized by treatment group for the safety set.

To assess tolerability, dose delay and dose reduction for the study treatment will be summarized by treatment group. By-patient listings will be provided.

Summary of duration of exposure of study treatment will include categorical summaries (based on clinically meaningful time intervals like < 4 weeks, 4-8 weeks, 8-12 weeks, >=12 weeks etc.) and continuous summaries (i.e. mean, standard deviation etc) using appropriate units of time.

The actual cumulative dose of the study treatment, DI, RDI and RDI categories to measure compliance will be summarized with descriptive statistics by treatment. The predefined

categories for RDI are $< 0.5, \ge 0.5 - < 0.75, \ge 0.75 - < 0.9, \ge 0.9 - < 1.1$ and ≥ 1.1 . The number and proportion of patients within each category will be presented by treatment group.

The number (%) of patients who have dose reductions or interruptions, and the reasons, will be summarized by treatment. Patient level listings of all doses administered on treatment along with dose change reasons will be produced.

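### The SAP's relative dose intensity divides both terms by the same actual duration, so late doses can never lower it, contrary to Protocol 10.3

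*SAP*

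**What the plan says.** Protocol 10.3 defines dose intensity (DI) as actual dose over actual duration, and RDI as "relative dose intensity (the ratio of dose intensity to planned dose/planned duration".

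SAP 3.2.1.9 also takes DI as actual cumulative dose over duration of exposure and RDI as DI divided by planned dose intensity (PDI). Its denominator differs: "Planned dose intensity (PDI) (mg/day) = planned cumulative dose (mg) / duration of exposure (days". Under SAP 3.2.1.4 that duration is an actual one. It runs from first administration to last date of exposure and includes temporary interruptions.

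SAP 3.2.1.8 describes planned cumulative dose as the "total dose planned to be given as per the protocol up to the last date of study treatment administration", but the calculation given is "For flat dosing: Planned cumulative dose (mg) = sum of (Dose prescribed, mg) for all infusions", with a parallel rule for weight-based dosing. The actual dose per infusion is the prescribed dose times volume administered over volume constituted.

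SAP 3.2.2 gives the use of the result: "RDI and RDI categories to measure compliance will be summarized with descriptive statistics by treatment". The categories run from below 0.5 to 1.1 and above, as in Protocol 10.3.

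**The concern.** RDI should show how far delivered dose per unit time fell short of plan. If numerator and denominator share one actual duration, the measure has no time dimension left. Protocol 6.1.1 makes timing a real route to lower intensity: "The next dose may be delayed by up to 7 days to recover from previous AEs".

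The SAP's other summaries do not fully replace it. Under SAP 3.2.1.5 a dose delay/interruption must have "a zero actual dose", so a dose given late but in full is not counted there. DI in mg/day does fall with delay, but in weight-based Phase I it also varies with body weight. On-time 3 mg/kg Q2W is 3 x 55 / 14 = 11.8 mg/day at 55 kg and 3 x 75 / 14 = 16.1 mg/day at 75 kg. What is lost is the normalized, categorized measure that the SAP presents as its measure of compliance.

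**Working it through.** The documents state no RDI figure to reproduce, so the check is algebra followed by worked cases.

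**Inputs.** Formulas: SAP 3.2.1.4, 3.2.1.8 and 3.2.1.9, and Protocol 10.3. Delay of up to 7 days per dose: Protocol 6.1.1. Intervals of 14, 21 and 28 days: the Q2W, Q3W and Q4W regimens. Dose levels of 1 and 0.3 mg/kg: Protocol Table 6-2. Assumption: the protocol does not define planned duration, so planned dose over planned duration is read as assigned dose per dosing interval. Any planned length gives the same rate.

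**Step 1: the SAP formula.** With D the duration of exposure, RDI = (actual / D) / (planned / D) = actual / planned. With p the prescribed dose and f the fraction of constituted volume given at each infusion, RDI = sum(p x f) / sum(p). This is a weighted fraction of volume infused. It cannot exceed 1 unless more volume is recorded as given than was constituted, so the top category (1.1 and above) is effectively unreachable.

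**Step 2: late but complete doses.** Every f = 1, so SAP RDI = 1.00. By the protocol, with n doses, interval T and k intervals each 7 days late, RDI = nT / (nT + 7k). Over six cycles nT is 168 days for Q4W (n = 6) and Q2W (n = 12), and 126 days for Q3W (n = 6).

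| k | Q4W or Q2W: 168/(168+7k) | Q3W: 126/(126+7k) | SAP |
|---|---|---|---|
| 1 | 0.960 | 0.947 | 1.00 |
| 2 | 0.923 | 0.900 | 1.00 |
| 3 | 0.889 | 0.857 | 1.00 |
| 4 | 0.857 | 0.818 | 1.00 |
| 5 | 0.828 | 0.783 | 1.00 |

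Over six cycles the value leaves the 0.9 to <1.1 category at k = 3. In a two-dose course one delay is enough: 56/63 = 0.889 (Q4W) and 42/49 = 0.857 (Q3W).

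**Step 3: reduced prescription.** Protocol Table 6-2 provides for one: "Dose level -1 represents a treatment dose for patients requiring a dose reduction from the starting dose level". If the prescription falls from 1 to 0.3 mg/kg for the last three of six complete, on-time infusions, protocol RDI = (3 x 1 + 3 x 0.3) / 6 = 0.65. The SAP gives 1.00, because the reduced prescription enters both sums. With incomplete infusions, a reduction can move SAP RDI either way, since it changes the weights p.

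**Step 4: skipped doses.** If two of eight slots between first and last dose are skipped, protocol RDI = 6/8 = 0.75. SAP RDI is also 0.75 if each skip is recorded as an infusion with a non-zero prescribed dose and zero volume given, and 1.00 if it is not. The documents do not say which applies. If nothing was constituted, the per-infusion formula is 0/0.

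**Step 5: testing a repair.** SAP 3.2.1.3 caps last exposure at death or cut-off. With an interval-based PDI and that cap kept, six on-time Q4W doses with death on day 10 of the last interval give 168 / (5 x 28 + 10) = 168/150 = 1.12. One Q4W dose with death on day 10 gives 28/10 = 2.80. Without the cap both are 1.00.

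Phase I patients may change regimen. Take on-time 1 mg/kg Q2W for four cycles, then 400 mg Q4W for four cycles, at an assumed weight of 70 kg. Against the initial dose throughout, RDI = (8 x 70 + 4 x 400) / (16 x 70) = 2160/1120 = 1.93 (2.50 at 50 kg, 1.61 at 90 kg). Scored by regimen segment it is 1.00.

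**The case against.** The strongest case on the other side is about scope.

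- **Terminology.** SAP 3.2.1.5 uses delay for a zero-dose record, and a skip of that kind may lower SAP RDI. But Protocol 6.1.1 separates a dose given late from one skipped, and the finding concerns the former. Skips stay conditional, as in step 4.
- **Size.** Over six cycles it takes three maximal delays to change category, and such delays are permitted, so scoring them as poor compliance is debatable. The size point stands. The second does not remove the mismatch with Protocol 10.3.
- **Other reporting.** The tolerability endpoint names dose intensity, not RDI. In flat-dosed Phase II (261 of 319 treated patients), DI can be read against 400/28 = 300/21 = 14.3 mg/day; with all five intervals 7 days late, Q4W gives 2400/203 = 11.8. Interruptions, reductions and dose listings are also reported. All of this stands and limits the severity.
- **Reduced prescriptions.** The 0.65 against 1.00 contrast requires the prescribed-dose field to hold the reduced dose. That is the natural reading, but the case report form is not available. Protocol Table 6-4 mostly resumes treatment without dose modification, so the case may be uncommon.
- **Planned duration is undefined.** True, but any planned length gives the same planned rate.

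**Conclusion.** The concern holds. As written, SAP RDI is not the quantity defined in Protocol 10.3, and the calculation in SAP 3.2.1.8 does not match its own description of planned cumulative dose. Late doses never lower SAP RDI. A reduced prescription does not lower it when infusions are complete. A skip lowers it only under a recording convention that the documents do not state. Over six cycles with five 7-day delays, the SAP reports 1.00 where the protocol gives 0.83 (Q4W or Q2W) or 0.78 (Q3W).

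This should be corrected, but it is confined to a descriptive exposure measure. DI and the interruption and reduction summaries survive, and the primary response analysis is unaffected. The figures assume complete infusions, the protocol's 7-day maximum delay, and planned dose over planned duration read as assigned dose per interval.

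**What to change.** In SAP 3.2.1.9, set PDI = planned dose per infusion / planned dosing interval (14, 21 or 28 days), and keep RDI as a ratio of actual to planned rate. Specify that:

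- For Phase I patients with a per-protocol dose escalation or regimen switch, RDI = actual cumulative dose / sum over regimen segments of (assigned dose / interval x days in segment). Other changes, including toxicity-driven adjustments, remain scored against the assigned regimen.
- For RDI only, duration = last administration + interval - 1 - first administration + 1, without the death and cut-off cap of SAP 3.2.1.3. A footnote should say that the RDI numerator therefore uses a different duration from the reported DI.
- The wording and calculation of planned cumulative dose in SAP 3.2.1.8 agree, and the SAP states how a skipped dose is recorded and counted.

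The cost is a small derivation change plus text edits, using dose, schedule and dates already collected. RDI values will become slightly less favourable, and any RDI in an earlier primary report would need a note on comparability. A hold still open at cut-off, or one that ends in discontinuation, will still not show, because the duration stops one interval after the last dose. Nothing in the change affects dosing or patient management.

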3.2.1.3 Last date of exposure to study treatment

PDR001every 2 weeks (Q2W) administration:

Last date of exposure = min(last date of administration of PDR001 + 13 days, death date, cut-off date).

PDR001 every 3 weeks (Q3W) administration:

Last date of exposure = min(last date of administration of PDR001 + 20 days, death date, cut-off date).

PDR001every 4 weeks (Q4W) administration:

Last date of exposure = min(last date of administration of PDR001 + 27 days, death date, cut-off date).

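### SAP relative dose intensity cancels time, so a full dose given late still scores 1.00, contrary to Protocol 10.3

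*SAP*

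**What the plan says.** Protocol 10.3 takes dose intensity (DI) as actual dose over actual duration and defines "relative dose intensity (the ratio of dose intensity to planned dose/planned duration". Two different durations appear in that one sentence.

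SAP 3.2.1.9 takes DI as actual cumulative dose over duration of exposure, then sets "Planned dose intensity (PDI) (mg/day) = planned cumulative dose (mg) / duration of exposure (days", and defines RDI as DI over PDI. Both terms use the same observed duration.

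SAP 3.2.1.8 describes the planned cumulative dose in words: it "is defined as the total dose planned to be given as per the protocol up to the last date of study treatment administration". It then gives the computing rule: "For flat dosing: Planned cumulative dose (mg) = sum of (Dose prescribed, mg) for all infusions". The weight-based rule has the same form. Actual dose per infusion is the prescribed dose times volume administered over volume constituted.

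SAP 3.2.1.3 ends exposure, for Q4W, at "Last date of exposure = min(last date of administration of PDR001 + 27 days, death date, cut-off date"; Q3W and Q2W use 20 and 13 days. SAP 3.2.1.4 leaves temporary interruptions inside the exposure duration.

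SAP 3.2.2 states the use: "DI, RDI and RDI categories to measure compliance will be summarized with descriptive statistics by treatment". The categories are cut at 0.5, 0.75, 0.9 and 1.1.

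Protocol 6.1.1 states: "The next dose may be delayed by up to 7 days to recover from previous AEs". If the dose cannot be given within that time, it is skipped.

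**The concern.** Relative dose intensity is meant to show how far the delivered rate of dosing fell below the planned rate. In this trial much of any shortfall should come through timing: Protocol Table 6-4 mostly tells sites to hold treatment and then resume at the same dose. With the duration cancelled, RDI measures only the fraction of the prescribed infusion volume that was given. A patient whose doses were full but repeatedly late is shown as fully dosed.

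The SAP states that it is based on Protocol Amendment 8, and its treatment section flags no departure from Protocol 10.3. Dose intensity is a named part of the secondary tolerability endpoint in Protocol Table 3-1. The SAP's count of delays and interruptions may not fill the gap, because SAP 3.2.1.5 requires "a zero actual dose"; a late full dose without such a record would not be counted there.

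**Working it through.** The documents give no worked RDI value, so there is none to reproduce.

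**Algebra.** Let A be the sum of actual doses, P the sum of prescribed doses over infusions, T the observed exposure and T_plan the planned duration.

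- SAP: RDI = (A/T) / (P/T) = A/P.
- Protocol 10.3: RDI = (A/T) / (P/T_plan) = (A/P) × (T_plan/T).

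**Inputs.**

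- Regimens: 400 mg Q4W and 300 mg Q3W (Phase II); Q2W (Phase I).
- T = last administration + 27, 20 or 13 days, minus first administration, + 1 (SAP 3.2.1.3 and 3.2.1.4).
- Delay of 7 days, the limit in Protocol 6.1.1.
- Assumption: T_plan is the sum of the planned dosing intervals.
- Assumption: six full infusions (A = P), with k of the five intervals 7 days late.

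**Controls.** With no delay both formulas give 1.000. With 10% of the volume lost and no delay both give 0.900. They differ only when timing changes.

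**Results, six full infusions.** The SAP value is 1.000 in every cell.

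| Regimen | Formula | k = 1 | k = 2 | k = 3 | k = 5 |
|---|---|---|---|---|---|
| Q4W | 168/(168+7k) | 0.960 | 0.923 | 0.889 | 168/203 = 0.828 |
| Q3W | 126/(126+7k) | 0.947 | 0.900 | 0.857 | 126/161 = 0.783 |
| Q2W | 84/(84+7k) | 0.923 | 0.857 | 84/105 = 0.800 | 84/119 = 0.706 |

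In mg/day, for Q4W with k = 5: DI = 2400/203 = 11.82. The SAP's PDI is also 2400/203 = 11.82, so RDI = 1.00. The planned rate is 2400/168 = 14.29, so RDI = 0.828.

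**Categories.** At k = 5 the two Phase II regimens belong in 0.75 to below 0.9 and Q2W in 0.5 to below 0.75; the SAP puts all three in 0.9 to below 1.1. At k = 2 both Phase II regimens are still in 0.9 to below 1.1; at k = 3 both have left it. Q2W leaves at k = 2.

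**Range for a single 7-day delay, from 2 to 12 infusions.** Q4W 0.889 to 0.980, Q3W 0.857 to 0.973, Q2W 0.800 to 0.960. After only two infusions one delay is enough to change category; after six it is not.

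**Skipped doses.** For one skipped dose of six scheduled (not the last), SAP RDI is 5/6 = 0.833 if the zero-dose row carries a prescribed dose and 5/5 = 1.00 if it does not. The documents do not say which.

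**The case against.** - **Planned duration is undefined and treatment is open-ended.** This stands: the values below 1.00 rest on an assumption. But the Protocol sets planned against actual duration in one sentence, which rules out using the observed duration for both.
- **The illustration is extreme and every delay in it is permitted.** This also stands. The documents give no delay frequency, so no number of misclassified patients can be inferred. One may argue that a compliance measure should not penalise permitted delays. That could justify a differently named measure, but not one that carries the Protocol's name and departs from its definition without saying so.
- **Other outputs show delay.** True: DI in mg/day falls as exposure lengthens, all doses are listed by patient, and AEs leading to dose interruption or adjustment are tabulated. This limits the harm but does not correct RDI.

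Two stronger readings are tempting and not supported. A reader might infer that SAP 3.2.1.8 contradicts itself, its wording counting doses due on the original calendar while its rule counts infusions. No text fixes planned doses to that calendar. SAP 2.1.3.4 says a rest period makes the cycle longer than planned, and on that basis wording and rule agree. A reader might also infer that RDI always misses skipped doses; that depends on a record layout not in the documents.

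**Conclusion.** The concern holds for dose timing. As written, SAP RDI is actual mg over prescribed mg and cannot respond to delay, contrary to Protocol 10.3. With planned duration taken as the sum of planned intervals, the largest discrepancy from permitted 7-day delays over six full infusions is 0.17 on Q4W, 0.22 on Q3W and 0.29 on Q2W (1.00 less 0.828, 0.783 and 0.706). Over six infusions a Phase II patient needs at least three late intervals of five to change category; shorter exposures need fewer.

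The reach is narrow: one descriptive secondary tolerability and compliance summary. It should be corrected because RDI is labelled a compliance measure and the data to compute it properly are already collected. It does not bear on the trial's efficacy or dose-finding conclusions.

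**What to change.** In SAP 3.2.1.9, set PDI = planned cumulative dose / planned duration. Define planned duration as the sum of the planned intervals (14, 21 or 28 days) for the dose and regimen planned at each infusion, with the last interval cut at death or data cut-off exactly as in SAP 3.2.1.3. Recompute RDI and its categories. Both details matter.

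- **Follow the regimen at each infusion.** Protocol 6.1.1 and 6.2.3.4 let Phase I patients escalate or switch to the RP2D after cycle 4. Take an assumed 70 kg patient on 1 mg/kg Q2W for four cycles, then 400 mg Q4W for four: (8 × 70 + 4 × 400)/224 = 2160/224 = 9.64 mg/day. Against the initially assigned 70/14 = 5 mg/day, RDI would be 1.93 with perfect dosing. Summing planned doses and intervals per infusion gives 1.00.
- **Truncate both sides alike.** For one 400 mg dose and death on day 14, DI = 400/14. Against an untruncated 400/28, RDI would be 2.00; with the planned interval also cut to 14 days it is 1.00. RDI stays equal to the reported DI over PDI.

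With a constant dose this also settles the skipped-dose example. PDI is 2000/140 or 2400/168, both 14.29 mg/day, so RDI = (2000/168)/14.29 = 0.833 whichever way the row is recorded.

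The cost is one formula and one sentence in a SAP amendment or addendum, using doses and dates already on the dosage administration record. No protocol amendment or new data are needed. At the least, if the present ratio is kept, record the departure from Protocol 10.3 and state in the table that the measure excludes dose timing.
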